- D. Unscheduled clinic visits are to be conducted in all cases of suspected symptomatic and asymptomatic VTE, progression/recurrence of VTE, paradoxical embolism (PDE), occurrence of post-thrombotic syndrome (PTS), major or clinically relevant bleeding events (MBEs / CRBEs) or other suspected significant AE or SAE. The unscheduled visit should be performed as soon as possible, preferably within 24 hours after the site first becomes aware of a suspected event. This visit should include all appropriate diagnostic procedures. If VTE progression/recurrence, PDE, PTS, MBEs, CRBEs are confirmed, the patient taking dabigatran etexilate is to be discontinued from the dabigatran etexilate treatment arm (eEOT visit to be performed as soon as possible), and an appropriate standard of care VTE treatment should be initiated per the investigator's discretion and/or local guidelines and the patient should be followed for the remainder of the study. If it is decided that a patient is to be discontinued from treatment due to an event, an eEOT visit should be conducted.
An unscheduled Visit is also to be performed in case a dabigatran etexilate dose adjustment is needed.
- E. The early End Of Treatment (eEOT) visit will be required for all patients who have taken a dose of dabigatran etexilate but failed to complete the full planned treatment observation period (completion of Visit 8). If feasible, this visit is also required for patients randomized to SOC should they decide to discontinue the trial or permanently stop SOC treatment for any reason. eEOT visit is not required if the SOC treatment is changed during the course of the trial.
- F. The informed consent (and if applicable assent) should be obtained per local legislations and guidelines from the patient's parent(s) or legal guardian and patient where applicable before any study procedures are performed. Should patients reach legal age during the trial they must personally sign and date the informed consent form as soon as possible and, at the latest, at the next visit
- G. Prior to start of therapy, all study inclusion and exclusion criteria must be checked to confirm patient eligibility.

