3.3.4 Removal of patients from therapy or assessments

3.3.4.1 Removal of individual patients

The parent(s) / legal guardian(s) and/or their child may decide to be removed from the study as follows:

- The patient/parent/legal guardian may decide to discontinue from treatment and wish to switch to another treatment prior to end of trial and be willing to be followed up within the clinical trial until the time at which study completion would have occurred.

Proprietary confidential information.

© 2019 Boehringer Ingelheim International GmbH or one or more of its affiliated companies. All rights reserved.

This document may not - in full or in part - be passed on, reproduced, published or otherwise used without prior written permission.

- The patient/parent/legal guardian may decide to discontinue study treatment or not participate in any further trial related activities, but be willing to be contacted once at a time point at which the patient would have completed the study to determine the patient's vital status.
- In very rare cases, the patient/parent/legal guardian may withdraw consent/assent to continue in the study for any reason; in doing so they refuse to participate in any further trial related activities and decline any contact or data to be collected for trial purposes. If this occurs, this decision must be clearly documented.

An individual patient is to be discontinued from trial treatment, but will remain part of the analysis population:

- If the patient is no longer able to participate for other medical reasons (e.g. surgery, AEs, other diseases or concomitant therapies).
- In the event that a new thromboembolic event or a clear clinical progression of the baseline VTE (e.g. based on ISTH guidelines) are observed as assessed by the Investigator and using appropriate imaging modalities or if the patient experiences a drug-related significant or drug-related serious AE or if drug toxicity is observed, then the patient is to be removed from the dabigatran treatment arm and be put on standard of care per investigator judgment and be followed until the end of the study. Subjects in the SOC arm may also require changes in their therapy.
- Patients who do not reach a total dabigatran plasma trough concentration within the pre-specified therapeutic range after one dose adjustment.

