The local product label and local treatment guidelines should be followed in case a major bleed is observed with a LMWH or a VKA or fondaparinux. For major bleeding under LMWH therapy, protamine sulphate will reverse about 75% of the effects of LMWH. With VKA, treatment should be temporarily stopped and the anticoagulant effect reversed with vitamin K, prothrombin complex concentrates and/or fresh frozen plasma. Readministration of SOC, after the bleeding has been resolved and haemostasis has been achieved, is at the discretion of the investigator.

Clinically relevant non-major bleeds or minor bleeds:

If a patient experiences a clinically relevant non-major bleed or minor bleed, dabigatran or SOC may be continued, temporarily interrupted or permanently discontinued, at the discretion of the investigator. It is not a requirement; however, that study drug is stopped in these cases.

Proprietary confidential information.

© 2019 Boehringer Ingelheim International GmbH or one or more of its affiliated companies. All rights reserved.

This document may not - in full or in part - be passed on, reproduced, published or otherwise used without prior written permission.

Management of dabigatran and SOC prior to and after planned surgery:

Dabigatran Treatment Discontinuation for Elective Surgical Interventions

For minor surgery or interventions with a low risk for bleeding per investigator judgment, elective procedures could take place 36 hours after the last dabigatran intake (two missed doses). Treatment can restart at investigator's discretion but not earlier than 2 days after minor surgical interventions.

For major surgery with high risk for bleeding per investigator judgment, interventions could take place at least 72 hours after the last dabigatran intake (5 missed doses). The decision to re-start treatment with dabigatran is at the investigator's discretion but should not occur prior to 7 days after major surgery. Patients should not re-start treatment with dabigatran after major surgery if there is a persistent increased risk of bleeding. The choice of alternative treatment is at the investigator's discretion. For minor procedures involving a critical organ such as lumbar or epidural punctures, interventions could only take place at least 72 hours after the last dabigatran intake (5 missed doses). The decision to re-start treatment with dabigatran is at the investigator's discretion but should not occur prior to 3 days after intervention.

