5.1.2.3 Bleeding assessment

Patients will be carefully assessed for signs and symptoms of bleeding.

The following definitions for bleeding are based on recommendations made by the Perinatal and Paediatric Haemostasis Subcommittee during the 56th-58th Scientific and Standardization Committee (SSC) Meetings of the ISTH ([R11-4225](#)).

Major bleeding:

- Fatal Bleeding
- Clinically overt bleeding associated with a decrease in haemoglobin of at least 2 g/dL (20 g/L) in a 24 hour period
- Bleeding that is retroperitoneal, pulmonary, intracranial, or otherwise involves the central nervous system
- Bleeding that requires surgical intervention in an operating suite

Clinically relevant non-major (CRNM) bleeding:

- Overt bleeding for which a blood product is administered and which is not directly attributable to the patient's underlying medical condition
- Bleeding that requires medical or surgical intervention to restore haemostasis, other than in an operating suite

Minor bleeding:

- Minor bleeds are any overt or macroscopic evidence of bleeding that does not fulfil the criteria for either major bleeding or clinically relevant, non-major bleeding

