5.2 SAFETY

5.2.1 Endpoints of safety

The main safety endpoint, freedom from major bleeding events (MBEs), is defined as either fatal bleeding; clinically overt bleeding associated with a decrease in haemoglobin of at least 20 g/L in a 24-hour period; bleeding that is retroperitoneal, pulmonary, intracranial or otherwise involves the central nervous system; or bleeding that requires intervention in an operating suite.

Other safety endpoints:

Proprietary confidential information.

© 2019 Boehringer Ingelheim International GmbH or one or more of its affiliated companies. All rights reserved.

This document may not - in full or in part - be passed on, reproduced, published or otherwise used without prior written permission.

- Incidence of bleeding events including:
 - Major bleeding events; clinically relevant non-major bleeding events (CRNM), minor bleeding events and any bleeding events
 - Combined endpoint of major and CRNM bleeding events
- Incidence of adverse events, protocol-specified AESI and serious adverse events
- Treatment discontinuation due to an adverse event
- Change from baseline in safety laboratory values, vital signs and physical examination
- Global assessment of tolerability (measured as treatment discontinuation and adherence) to study medication

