7.3.3 Safety analyses

Major bleeding events will be analysed as a secondary endpoint. All bleeding events and combined endpoint of major and clinical-relevant bleeding events will be analysed by the Cox proportional hazards model with treatment being the factor and stratified by age group if appropriate. Pooling of age groups or non-stratified analysis might be performed if the event rate is low. All safety analyses as well as all bleeding events and all-cause mortality analysed as efficacy endpoints will be performed on the treated set.

The safety analysis set will include all randomized patients who take at least one dose of study medication. Patients in the safety population will be analysed according to the study treatment they have received. The safety analyses will be descriptive in nature and will be based on BI standards. The safety analyses will include the following parameters:

- All AEs
- protocol-specified AESI
- serious AEs
- AEs leading to treatment discontinuation

AEs will be coded using the MedDRA dictionary. All AEs will be classified according to the following trial periods: screening, on-treatment, post treatment. All AEs with an onset date/time after the 1st dose of trial medication up to 6 days after the last intake of study medication will be assigned to the treatment period for evaluation. In addition, AEs with onset date before start of the trial treatment but with worsening in intensity during the treatment will also be assigned to the on-treatment period. Other AEs will be assigned to the screening or post-treatment period, respectively. All AEs (including bleeding) in the treatment period will be tabulated in total and according to seriousness, severity and possible relationship to trial medication. AEs in the screening or follow-up period will be listed.

Other lab data, vital signs, physical examinations data and ECG data will be reported descriptively.

Proprietary confidential information.

© 2019 Boehringer Ingelheim International GmbH or one or more of its affiliated companies. All rights reserved.

This document may not - in full or in part - be passed on, reproduced, published or otherwise used without prior written permission.

Proprietary confidential information.

© 2019 Boehringer Ingelheim International GmbH or one or more of its affiliated companies. All rights reserved.

This document may not - in full or in part - be passed on, reproduced, published or otherwise used without prior written permission.

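### Flow Chart footnote D orders dabigatran stopped after a confirmed clinically relevant bleed, while Section 4.2.1 lets the investigator continue it after a non-major one

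*Protocol*

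**What the plan says.** **Flow Chart footnote D (Protocol).** An unscheduled visit is required for a list of suspected events that includes major bleeding events (MBEs) and, as a separate item, clinically relevant bleeding events (CRBEs). Then: "If VTE progression/recurrence, PDE, PTS, MBEs, CRBEs are confirmed, the patient taking dabigatran etexilate is to be discontinued from the dabigatran etexilate treatment arm". An early end-of-treatment (eEOT) visit follows and standard of care (SOC) is started. The investigator's discretion covers the choice of SOC, not whether dabigatran stops. The paragraph on events ends: "If it is decided that a patient is to be discontinued from treatment due to an event, an eEOT visit should be conducted".

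**Section 4.2.1 (Protocol).** For a major bleed dabigatran must be stopped, which agrees with footnote D. For a CRNM or minor bleed, "dabigatran or SOC may be continued, temporarily interrupted or permanently discontinued, at the discretion of the investigator", followed by "It is not a requirement; however, that study drug is stopped in these cases".

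**Related text.**
- Section 5.1.2.3 defines three classes only: major bleeding, "Clinically relevant non-major (CRNM) bleeding" and minor bleeding.
- Section 5.2.1 lists the endpoint "Combined endpoint of major and CRNM bleeding events". Section 7.3.3 calls the same analysis the "combined endpoint of major and clinical-relevant bleeding events".
- Section 3.3.4.1 requires removal from dabigatran "if the patient experiences a drug-related significant or drug-related serious AE or if drug toxicity is observed", without saying whether a CRNM bleed can qualify.
- SAP Table 6.2: 1, code Z3, repeats that removal criterion. No deviation code names a CRNM bleed.

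**The concern.** These are two current instructions on whether to stop an anticoagulant in a child who has bled, and they differ. Section 6.1 of the protocol sends sites to the Flow Chart for required procedures, so staff working from it meet the mandatory stop. Staff who consult the section on bleeding management meet discretion.

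Either mistake reaches a patient. One is an unneeded switch off assigned treatment. The other is continued dosing where a stop was intended.

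Footnote D's stop binds only the dabigatran arm. After a CRNM bleed, SOC patients remain under investigator discretion, so the choice of rule acts on one arm only. It would change:
- the frequencies of permanent discontinuation and of switching from dabigatran to SOC (Protocol 7.3.2, SAP 7.5.2);
- exposure (SAP 7.7);
- the treatment period to which later adverse events are assigned (SAP 7.8.1);
- the number completing three months of dabigatran (Protocol 7.6);
- the date of the thrombus-progression reading, which is the earlier of Day 84 and the eEOT visit (Protocol 5.1.1, SAP 7.5.2).

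**Working it through.** The main check is a comparison of texts. The plan gives no figure of its own on this point.

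**1. Does CRBE cover CRNM bleeds?** The term is not in the abbreviation list, so this is an inference. Three points support it:
- Footnote D lists CRBEs apart from MBEs. If CRBE meant major bleeds only, the second item would add nothing.
- Section 5.1.2.3 has one class besides major that is called clinically relevant, namely CRNM.
- Section 7.3.3 writes "combined endpoint of major and clinical-relevant bleeding events" where Section 5.2.1 writes "Combined endpoint of major and CRNM bleeding events", so the protocol already uses clinically relevant as shorthand for CRNM.

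If CRBE meant major and CRNM bleeds together, the result for CRNM would be the same.

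**2. The rules side by side, for a patient on dabigatran**

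| Confirmed event | Footnote D | Section 4.2.1 | Agree? |
|---|---|---|---|
| Major bleed | Stop | Stop | Yes |
| CRNM bleed | Stop | Continue, interrupt or stop | No |
| Minor bleed | Not named | Continue, interrupt or stop | No conflict |

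**3. What a site can do after a CRNM bleed.** Permanent discontinuation satisfies both texts. Continuing, or interrupting and restarting, satisfies Section 4.2.1 and breaches footnote D.

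**4. Does any other text reconcile them?**
- Footnote D's closing sentence ("If it is decided that a patient is to be discontinued from treatment due to an event, an eEOT visit should be conducted") says when an eEOT visit is held. It does not withdraw the stop.
- Section 3.3.4.1 turns on whether the event is drug-related and significant. Footnote D asks neither question. Section 3.3.4.1 therefore adds a third, overlapping test and does not decide between the other two.
- The SAP deviation list and the amendment log contain nothing that aligns the rules.
- Figure 4.2.1: 1, on managing bleeding, is not reproduced in the available text and could not be checked.

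**5. Size per patient.** Inputs from Protocol 7.6 are 94 patients planned on dabigatran and a discontinuation rate of up to 15% before three months.
- One extra stop: 1/94 = 0.0106, or 1.1 percentage points.
- Discontinuations implied by the planned rate: 0.15 × 94 = 14.1.
- One extra stop relative to that: 1/14.1 = 7.1%.

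The 15% is an upper value estimated for this trial and trial 1160.108 together, so the last ratio is only a scale reference. How often the rules would diverge cannot be computed without a CRNM rate.

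**6. Effect on the main analyses.** SAP 7.4 uses thrombus assessments made after the eEOT visit, up to Day 84 + 7 days, for patients who switch from dabigatran to SOC, so the primary intention-to-treat analysis is largely protected. On-treatment follow-up for major bleeding might change, but SAP 6.1 defines that window by trial treatment (dabigatran or SOC) and does not settle it for switched patients. No figure is claimed for it.

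**The case against.** The strongest reply is that Section 4.2.1 is the dedicated bleeding section, addresses CRNM bleeds by name, and says outright that stopping is not required. A careful reader would follow it and treat footnote D as loose shorthand built on an undefined abbreviation. Footnote D's closing sentence would also be partly redundant for dabigatran patients if every listed event forced a stop. The unseen figure may state the CRNM rule plainly.

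Much of this supports the direction of the fix. It does not remove the conflict, because the protocol gives no rule of precedence and the closing sentence may equally concern SOC patients or other adverse events.

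Several narrower objections stand:
- One patient in 94 is what any patient contributes to a proportion. It says nothing about how often the rules diverge.
- Discontinuation, switching and thrombus progression are summarised descriptively. Reasons for discontinuation and switching are reported, so stops caused by bleeding can be identified.
- The three-month completion figure is a planning projection across two trials, not an analysis of this one.
- Adverse-event period assignment follows the actual last dabigatran dose and is well defined under either rule.
- The arms are also treated differently after major bleeds, by design, so asymmetry alone is not the defect.
- That Section 3.3.4.1 does not name CRNM bleeds shows little about intent, since it does not name major bleeds either.

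**Conclusion.** The concern holds. For a confirmed CRNM bleed on dabigatran, footnote D and Section 4.2.1 give different instructions, and no other text in the protocol or SAP reconciles them. The conclusion rests on reading CRBE as including CRNM, which is an inference, though the alternative reading leaves the term with no function. It is also subject to the content of Figure 4.2.1: 1.

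The total effect cannot be sized from the documents. The statistical consequences fall mainly on descriptive secondary and safety outputs. Sample size, margin and significance level are unaffected. The reason to correct the text is mainly patient safety and uniform conduct: sites should not hold contradictory orders on stopping an anticoagulant after a bleed. It should be corrected, but it does not threaten the main conclusion of the trial.

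**What to change.** State one rule everywhere.

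**Default, following the more specific text:**
- In footnote D, limit the mandatory stop for bleeding to MBEs.
- Keep CRNM bleeds as a trigger for an unscheduled visit, with treatment handled as in Section 4.2.1.
- Replace CRBE with CRNM.
- State in Section 3.3.4.1 whether a drug-related CRNM bleed counts as a significant drug-related adverse event.

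**If the sponsor intends a mandatory stop:** amend Section 4.2.1 and Section 3.3.4.1 to say so, and add a matching code to the SAP deviation list.

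In either case, confirm that Figure 4.2.1: 1 shows the same rule.

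**Cost.** A short protocol amendment, which needs ethics committee and authority approval (Protocol 8.1) and can be included in the next one. No new data are needed, because reasons for discontinuation and switching are already recorded and reported (Protocol 3.3.4.1, SAP 7.5.2 and 7.7).
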